research unit. Prior to discharge, the plasma glucose (measured by YSI) must be between 80 and 200 mg/dL on the final two measurements, taken at least 30 minutes apart. If the plasma glucose is between 80 and 90 mg/dL then the CGM trend arrow must be either stable or increasing during the last 30 minutes of observation.

When the standard meal is consumed, the Omnipod® pump will be removed and the site will be assessed visually using the Draize scale. Prior to discharge, the sensors will be removed to permit analysis of timing of alerts and the site of the Omnipod insertion will be reassessed using the Draize scale.

Blood samples collected during this visit will be processed and stored at -80 for subsequent analysis of insulin, glucagon and incretin hormone levels to assess endogenous responses (vehicle delivery days) as well as post-bolus plasma levels (glucagon delivery days). The patient will be called by a study team member within 24 hours of the study visit to collect data for symptoms, glucose values, and any adverse events following study visit.

Between one to two weeks following visit day 3, patient will be scheduled for visit day 5.

Visit Day 4 (Optional): Two to three days prior to visit day 5, patient will have an **optional** visit day 4, during which two Dexcom sensors will be placed on the anterior abdominal wall. If the study team and patient are comfortable with sensor placement, sensor placement can occur at home instead, again 2-3 days before visit day 5. The time of sensor placement will be documented by a phone call by a member of the study team and the study physician will review the medication, food and activity recommendations in preparation for study visit 5.

Study Visit Day 5: Mixed Meal Testing: This visit will be identical to visit 3 with the exception that the patient will receive the other treatment (either vehicle or glucagon) during the mixed meal tolerance test when a hypoglycemic event is predicted by the controller algorithms. As with study visit day 3, the patient will be called by a study team member within 24 hours of the study visit to collect data to survey symptoms, glucose values and for any adverse events following study visit.

Part 2: Testing control system for sensor-guided delivery of glucagon via closed-loop system to prevent post-exercise hypoglycemia in patients with post-bariatric hypoglycemia

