4. DATA ANALYSIS / SUBJECT SELECTION

Subject Selection:

Approximately 40 subjects may be screened for this study, assuming approximately 30% will not meet inclusion criteria, and assuming 20% dropout rate. The goal is for 20 subjects to complete Part 1 and Part 2 studies. To allow for potential drop-outs, 28 subjects will be randomized.

Data Analysis:

All subjects who have received at least one dose of glucagon will be included in the data analysis set. Adverse events, vital signs, physical examination, laboratory safety variables (Screening to Final Visit), EKG (Screening to Final Visit), and local tolerability data will be reviewed and summarized on an ongoing basis during the study to evaluate the safety of subjects. Safety data will be presented in tabular and/or graphical format and summarized descriptively, where appropriate.

Sensor and glucagon or vehicle delivery information will be collected and evaluated for specificity and response time.

Plasma glucagon concentrations will be analyzed by a validated LCMS method in a GLP compliant lab (Celerion, Inc. Lincoln, NE). Insulin and incretin plasma concentration profiles will be analyzed with a commercially available radioimmunoassay method (RIA, Millipore) and analyzed using repeated-measures ANOVA.

The primary endpoint for this study is prevention of meal or exercise-provoked hypoglycemia, defined as glucose levels below <65 mg/dl, compared to vehicle control. Secondary outcome measures will compare outcomes for glucagon versus vehicle infusions for the following metrics including: (1) prevention of severe hypoglycemia (defined as glucose levels below 60 mg/dl); (2) prevention of rebound hyperglycemia (defined as glucose levels above 180 mg/dl); (3) time in goal range (65-180 mg/dl), reported in minutes.

Success will be defined as meeting the primary endpoint in 12 of 20 participants. If this is not achieved, the algorithm will be revised, and an additional 5 participants may be recruited for additional study.

Data will be analyzed after 10 individuals have completed the paired analysis of response to glucagon vs. vehicle. At that time, power will be determined, and sample size will be adjusted if needed.

Local Interim Data Analysis/Data Monitoring Plan

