If at any time during the study visit the glucose level falls to or below 55 mg/dl (i.e. as a result of vehicle delivery on vehicle treatment days, inadequate trigger, or inadequate pump-delivered glucagon response), or if the patient develops neuroglycopenia, or if the participant develops severe discomfort with signs and symptoms of hypoglycemia, then the closed-loop pump will be deactivated and treatment for clinically significant hypoglycemia [34] will be initiated. If the participant's previously established IV line is functional, one ampule of D50 (25 grams in 50 mL, 50% glucose solution) will be administered over 2-5 minutes via the intravenous line. Glucose will be re-measured every 5 minutes and intravenous glucose will be given every 15 minutes until blood glucose is > 54 mg/dL and neuroglycopenia is resolved, or more frequently at the discretion of the study physician. If clinically significant hypoglycemia develops and the previously established intravenous lines are non-functional then the study nurse or physician will administer 1.0 mg of commercial glucagon subcutaneously. The study nurse will also attempt to re-establish intravenous access, while glucose will continue to be measured every 5 minutes. Intravenous glucose may be used to resolve persistent neuroglycopenia or for glucose levels ≤ 54 mg/dL. If 2 doses of intravenous glucose are required, an infusion of 10% dextrose will be initiated at a rate of 100 mL/hour, and glucose levels will be monitored every 10 minutes and rate adjustments will be made according to glucose results. Once glucose levels are above 100 mg/dL, intravenous infusion will be tapered with continued monitoring as indicated clinically by the study physician.

If after treatment for clinically significant hypoglycemia the glucose remains < 70 mg/dL but > 54 mg/dL, neuroglycopenia is resolved, and if the patient is able to swallow, then the team will administer oral glucose 15-30 grams (glucose tablets or gel). If the patient is unable to tolerate oral intake (e.g. due to nausea), the team will administer $\frac{1}{2}$ ampule of D50 (12.5 grams in 25 mL) over 2-5 minutes intravenously. Once hypoglycemia has resolved (glucose > 70 mg/dL), neuroglycopenia has resolved, and patient is able to swallow, then the team will provide a standard lunch meal containing complex, low-GI carbohydrates, fat and protein to maintain euglycemia.

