The study visit will also be halted if the participant develops unremitting nausea, abdominal pain, or wishes to discontinue the study for any reason.

If hypoglycemia does not ensue by 180 minutes (highly unlikely with this protocol), the subject will be provided a standard meal.

Following the standard lunch meal, venous blood glucose will be monitored every 15 minutes for a minimum of 2 hours and then every 30 minutes until the time of discharge. The time of discharge will be set at 6.5 hours after the mixed meal test to ensure stability prior to discharge from the clinical

Approved by

JDC CHS

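### The primary endpoint is a comparison with vehicle, but success is a 12-of-20 count with no per-participant scoring rule and no test of that comparison

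*Combined protocol and SAP*

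**What the plan says.** All of the following is in the combined protocol and SAP.

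- **Endpoint (section 4, Data Analysis).** "The primary endpoint for this study is prevention of meal or exercise-provoked hypoglycemia, defined as glucose levels below <65 mg/dl, compared to vehicle control".
- **Success (same section).** "Success will be defined as meeting the primary endpoint in 12 of 20 participants". If the count is missed: "If this is not achieved, the algorithm will be revised, and an additional 5 participants may be recruited for additional study".
- **Design (Part 1, Study Visit Day 5).** Part 1 is a two-visit crossover. Of Visit Day 5 the plan says: "This visit will be identical to visit 3 with the exception that the patient will receive the other treatment (either vehicle or glucagon".
- **Paired analysis (section 4).** It appears once, for an early look: "Data will be analyzed after 10 individuals have completed the paired analysis of response to glucagon vs. vehicle". Power is to be worked out then and the sample size changed if needed. No test, significance level or sidedness is given.
- **Named methods (section 4).** The only one is repeated-measures ANOVA, for insulin and incretin profiles.
- **Analysis set (section 4).** "All subjects who have received at least one dose of glucagon will be included in the data analysis set".
- **Expected vehicle result (Part 1 meal visit).** "If hypoglycemia does not ensue by 180 minutes (highly unlikely with this protocol), the subject will be provided a standard meal". No rate is given.
- **Rescue (Part 1, treatment of clinically significant hypoglycemia).** Besides a glucose trigger of 55 mg/dl, rescue starts on neuroglycopenia, "or if the participant develops severe discomfort with signs and symptoms of hypoglycemia, then the closed-loop pump will be deactivated".
- **Exercise (Part 2).** The purpose paragraph and the start of the exercise visit describe a pump filled with glucagon. Later paragraphs of the same part speak of a vehicle bolus and of vehicle days.

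**The concern.** A count of participants out of 20 is not a comparison with vehicle until the plan says how each person's two visits are combined. The supplied text allows at least two readings.

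- **Both visits:** a participant counts if glucose falls below 65 mg/dl on vehicle and does not on glucagon. Participants who do worse on glucagon are simply not counted, and those with no event on vehicle cannot contribute.
- **Glucagon visit only:** a participant counts if glucose stays at or above 65 mg/dl on glucagon. Vehicle plays no part.

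The same data can pass on one reading and fail on the other, and the choice could be made after the data are seen. At stake is whether the headline result answers the stated question. For exercise there is a further doubt: whether a vehicle comparison exists at all.

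**Working it through.** **Inputs from the plan.** 20 completers; success at 12 (12/20 = 60%); event threshold 65 mg/dl; two visits per person in Part 1. The 12 cannot be re-derived, because no null rate, significance level, power or effect size is stated.

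**Assumptions.** g and v are the event-free proportions on glucagon and vehicle; the plan gives neither. f is the probability of a favourable pair (event on vehicle, none on glucagon) and r that of a reverse pair. Two within-person structures bracket the range:

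- independent visits: f = g(1 − v), r = v(1 − g)
- no reverse pairs: f = g − v, r = 0

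Rule met = P(Bin(20, f) ≥ 12). McNemar power is by exact trinomial enumeration over 20 pairs, two-sided 5%, counting results in favour of glucagon.

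**1. Single outcomes on the both-visits reading.** Exact McNemar p, favourable v reverse: 6 v 0 = 0.031; 8 v 1 = 0.039; 10 v 2 = 0.039; 11 v 0 = 2 × 0.5^11 = 0.001. All fail the rule. Conversely, 12 v 4 (p = 0.077) and 12 v 8 (p = 0.50) pass it, because reverse pairs are ignored. Passing without significance is rare: below 0.5% in every scenario tabulated below.

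**2. Both-visits reading, operating characteristics.** Worked case, g = 0.70, v = 0.05:

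- independent: f = 0.70 × 0.95 = 0.665, r = 0.05 × 0.30 = 0.015; rule 80.5%, McNemar 99.4%
- no reverse pairs: f = 0.70 − 0.05 = 0.65; rule 76.2%, McNemar 99.97%

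| g | v | Rule met (independent / no reverse) | McNemar power (independent / no reverse) |
|---|---|---|---|
| 70% | 0% | 89% / 89% | 100% / 100% |
| 70% | 5% | 81% / 76% | 99% / 100% |
| 70% | 10% | 70% / 60% | 97% / 99.8% |
| 70% | 20% | 45% / 25% | 83% / 98% |
| 70% | 30% | 22% / 6% | 59% / 87% |
| 80% | 5% | 97% / 96% | 100% / 100% |
| 90% | 5% | 99.9% / 99.9% | 100% / 100% |

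With no drug effect and independent visits, f = q(1 − q) ≤ 0.25, so the rule is met in at most P(Bin(20, 0.25) ≥ 12) = 0.1% of trials. Positive correlation between visits lowers this further.

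**3. Glucagon-visit-only reading, no drug effect.** With a common event-free rate q, P(Bin(20, q) ≥ 12) is 5.7% at q = 40%, 25% at 50% and 60% at 60%. It is 0.5% at q = 30% and effectively zero at q = 5%.

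**4. Which rows are plausible.** The Part 1 text treats a meal visit without hypoglycemia as very unlikely, which points to small v. That sentence does not define hypoglycemia as below 65 mg/dl and gives no rate, so 5% is an assumption.

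**5. Part 2.** Set side by side, the purpose paragraph and pump set-up provide for glucagon only, while the delivery and rescue paragraphs provide for vehicle. The exercise half of the endpoint needs a vehicle visit that the supplied text neither clearly schedules nor rules out.

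**The case against.** The strongest reply is that the two rules ask different questions. Twelve of 20 asks whether most participants are protected; McNemar asks whether the effect differs from zero. Six favourable pairs and no reverse pairs is significant with only 6/20 = 30% benefiting. Missing the count leads to algorithm revision, so a bar stricter than significance can be a deliberate development criterion. This stands, and it is why 12 of 20 should be kept for that purpose. It does not turn the count into a test of the vehicle comparison, and section 4 presents it as success on the primary endpoint.

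Three stronger readings are tempting, and the documents support none of them.

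- *A working algorithm would probably be declared a failure.* The large gaps need 20–30% event-free vehicle visits, which sits poorly with the plan's own expectation and with an eligible population that has ongoing hypoglycemia despite diet and acarbose. Nor is it an error to revise an algorithm that protected 11 of 20, if 60% was the intended bar.
- *The rule passes an ineffective treatment.* That needs the glucagon-visit-only reading and a high event-free rate on vehicle.
- *The up to 5 extra participants inflate false success.* Section 4 does not say that they count toward the result, so no error rate can be attached to them.

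A scoring rule may also stand in the missing opening of Part 1. Section 4, where one would expect it, has none.

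**Conclusion.** The point holds as a gap in the primary analysis. The plan states a comparison with vehicle and decides success by a count that, in the supplied text, either leaves vehicle out or disregards reverse pairs, with no test of the comparison.

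Its size depends on vehicle rates that the plan does not give. In the range its own text makes likely (about 5% event-free on vehicle, assumed), the both-visits reading falls short of a paired test by roughly 18 to 24 percentage points if glucagon keeps 70% event-free, by 3 to 4 points at 80%, and by almost nothing at 90%. False success on the glucagon-only reading is then negligible. Both errors grow if event-free vehicle visits are more common than expected. All figures assume 20 fixed pairs, although section 4 allows the sample size to change after 10.

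This should be fixed. Confidence is moderate, because of the missing Part 1 text and the assumed rates.

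**What to change.** 1. **Primary inference for the Part 1 crossover.** Use a two-sided 5% exact paired test (McNemar, or a version that allows for period) on any glucose below 65 mg/dl per visit, with the paired risk difference and its confidence interval.
   - State the glucose source and time window, unless the missing Part 1 text already does.
   - State how rescued visits are scored. Rescue can start on symptoms alone, so a visit rescued at or above 65 mg/dl would otherwise count as event-free.
   - Use participants with both visits, and say that this differs from section 4's set, which can include someone with no vehicle visit.
   - State how the test and the 12-of-20 trigger apply if the sample size changes after the look at 10 pairs.
2. **Keep 12 of 20 as the go/no-go trigger** for revising the algorithm, with its per-participant definition written out. Report the up to 5 revised-algorithm participants separately from the primary result.
3. **Reconcile the Part 2 paragraphs** on whether there is a vehicle visit, and say whether 12 of 20 applies to each part or overall. If Part 2 has no vehicle visit, report exercise results descriptively and limit the vehicle-controlled claim to meals.

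**Cost.** These are wording changes on data already to be collected, with no extra participants or visits. The 12-of-20 headline becomes secondary and the primary claim may narrow to meals. A period-adjusted exact test (Mainland-Gart with Fisher's exact test, 10 per sequence, no true period effect) costs some power. At g = 70% and v = 10/20/30% it gives 95/79/54% (independent) or 99/93/74% (no reverse pairs), against McNemar 97/83/59% or 99.8/98/87%.

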12. Where and how will your project utilize the Joslin Diabetes Center?

■ **General Clinical Research Center (GCRC)**

Primary site

Clinical Trials Unit (CTU)

■ **Joslin Clinic**

Eye Unit

Other (please specify) _____

13. Will your project involve research on living human fetuses?

Yes

■ **No**

14. Does your project involve the use of any new drug or device?

■ **Yes** IND# 120653 (Xeris Pharmaceuticals) ; IDE # G170159

No

15. Is review required by risk management foundation?

Yes

■ **No**

Signature of Principal Investigator

Date

I have read and reviewed this application for approval by the Committee on Human Studies

Signature of PI's Section Head

Date

Please bring the original and twenty-four (24) copies of this form and the informed consent form for the above research project to [name] in the Office of Sponsored Research by the appropriate CHS meeting deadline.

Approved by
JDC CHS 

If the closed-loop system generates a second hypoglycemia alarm within the two hour observation period but after a lockout period (15 minutes if sensor glucose is ≤ 60 mg/dL or 30 minutes if sensor glucose > 60 mg/dL), then the closed-loop system will deliver a second dose of study drug. The volume of the second dose of study drug will be either 6 or 3 units, equivalent to either 300 or 150 μ g of glucagon) as per system algorithm delineated in **Table 1**, above.

- 6 units of study drug if sensor glucose is < 65 mg/dL
- 6 units of study drug if sensor glucose is ≥ 65 mg/dL but < 75 mg/dL, and rate of change of sensor glucose is negative. If sensor glucose rate of change is positive within this range of glucose, no study drug is given.
- 3 units of study drug if sensor glucose is ≥ 75 mg/dL and < 100 mg/dL.
- 3 units of study drug if sensor glucose is ≥ 100 mg/dL and ≤ 150 mg/dL and a meal is detected by the algorithm. If no meal is detected, no bolus will be delivered.

Plasma glucose will be monitored by YSI every 5 minutes for an additional 30 minutes, and insulin and glucagon levels will be analyzed concurrently. Lunch will be provided 120 minutes after the initial study drug treatment or 30 minutes after the second study drug treatment, whichever occurs later.

If at any time during the study visit the glucose level falls to or below 55 mg/dl (i.e. as a result of vehicle delivery on vehicle treatment days, inadequate trigger, or inadequate pump-delivered glucagon response), or if the patient develops neuroglycopenia, or if the participant develops severe discomfort with signs and symptoms of hypoglycemia, then the closed-loop pump will be deactivated and treatment for clinically significant hypoglycemia [34] will be initiated. If the participant's previously established IV line is functional, one ampule of D50 (25 grams in 50 mL, 50% glucose solution) will be administered over 2-5 minutes via the intravenous line. Glucose will be re-measured every 5 minutes and intravenous glucose will be given every 15 minutes until blood glucose is > 54 mg/dL and neuroglycopenia is resolved, or more frequently at the discretion of the study physician. If clinically significant hypoglycemia develops and the previously established intravenous lines are non-functional then the study nurse or physician will administer 1.0 mg of commercial glucagon subcutaneously. The study nurse will also attempt to re-establish intravenous access, while glucose will continue to be measured every 5 minutes. Intravenous glucose may be used to resolve persistent neuroglycopenia or for glucose levels ≤ 54 mg/dL. If 2 doses of intravenous glucose are required, an infusion of 10% dextrose will be initiated at a rate of 100 mL/hour, and glucose levels will be monitored every 10 minutes and rate adjustments will be made according to glucose results. Once glucose levels are above 100 mg/dL, intravenous infusion will be tapered with continued monitoring as indicated clinically by the study physician.

If after treatment for clinically significant hypoglycemia the glucose remains < 70 mg/dL but > 54 mg/dL, neuroglycopenia is resolved, and if the patient is able to swallow, then the team will administer oral glucose 15-30 grams (glucose tablets or gel). If the patient is unable to tolerate oral intake (e.g. due to nausea), the team will administer $\frac{1}{2}$ ampule of D50 (12.5 grams in 25 mL) over 2-5 minutes intravenously. Once hypoglycemia has resolved (glucose > 70 mg/dL), neuroglycopenia has resolved, and patient is able to swallow, then the team will provide a standard lunch meal containing complex, low-GI carbohydrates, fat and protein to maintain euglycemia.

The study visit will also be halted if the participant develops unremitting nausea, abdominal pain, or wishes to discontinue the study for any reason.

If hypoglycemia does not ensue by 180 minutes (highly unlikely with this protocol), the subject will be provided a standard meal.

Following the standard lunch meal, venous blood glucose will be monitored every 15 minutes for a minimum of 2 hours and then every 30 minutes until the time of discharge. The time of discharge will be set at 6.5 hours after the mixed meal test to ensure stability prior to discharge from the clinical

Approved by

JDC CHS
